### **1.6 Circulating Tumor Cells (CTCs) to assess TRAIL receptor expression**

CTCs will be isolated by a novel microfluidics CTC platform (VERSA Chip) that integrates CTC capture (>90% efficiency) with quantitative immunofluorescence and nucleic acid extraction/analysis[34-39]. CTCs will be captured using multiple antibodies (EpCAM, cell surface vimentin, MUC1, and CD133) determined by analysis of CTCs isolated in preclinical studies. Captured CTCs will be analyzed by quantitative immunofluorescence (TRAIL, TRAIL-R1 and TRAIL-R2) followed by RT-PCR analysis of mRNA levels of these targets using the VERSA Chip[37, 38].

CTCs will be drawn and analyzed if funding is secured.

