### **2.2 Secondary Objectives:**

2.2.1 To determine progression-free survival (PFS) to ONC201 with a methionine-restricted diet in patients with metastatic TNBC.

2.2.2 To determine clinical benefit rate (complete and partial response plus stable disease) (CBR) at 4 months to ONC201 with a methionine-restricted diet in patients with metastatic TNBC.

2.2.3 To determine overall survival (OS) to ONC201 with a methionine-restricted diet in patients with metastatic TNBC.

2.2.4 To determine the safety of adding a methionine-restricted diet to ONC201 in patients with metastatic TNBC

2.2.4 To assess metabolic indices in patients with metastatic TNBC treated with ONC201 and a methionine-restricted diet.

2.2.5 To assess the expression of TRAIL receptor in CTCs prior, during and upon progression in patients with metastatic TNBC treated with ONC201 with a methionine-restricted diet.

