### **8.2 Circulating tumor cells (CTCs)**

If funding is secured, CTCs will be enumerated and evaluated for TRAIL expression. We hypothesize that treatment with MR diet will increase the expression of TRAIL receptors on CTCs and reduce the number of CTCs.

**Time points:** CTCs will be collected at baseline, on day 5 of cycle 2, and at end of treatment. If the CTC sample is not collected at baseline, the remaining samples should not be collected. Missed CTC samples will not be considered a protocol deviation.

Please note that CTC samples must be shipped Monday –Thursdays only. Samples must be shipped to arrive at the [name] lab by Fridays by 12:00 p.m. CTC samples will be drawn only at those sites identified by the coordinating site as having adequate resources (shipping and funding) to provide the samples.

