### 13.7.2 Analysis plans for secondary objectives

PFS and OS will be summarized using Kaplan-Meier estimates of the median survival times. Point estimates as well as 95 % confidence intervals will be provided. PFS based on degree of AR expression by IHC (AR >0% vs. AR  $\geq$ 10%) will be compared using the log-rank test. Additional exploratory analyses using proportional hazards model to control for other factors may be performed.

CBR at 4 months will be estimated according to RECIST 1.1, by dividing the total number of responders (complete plus partial responses plus CR or PR or stable disease (SD)), by number of subjects with measurable disease and the exact 95% confidence interval will be provided. In evaluating CBR, subjects with missing data will be considered non-responders. Also, duration of response (DOR) will be measured using Kaplan-Meier methodology. A 95% confidence interval will be provided for the median duration of response. Subjects who do not relapse will be censored at the day of the last objective tumor assessment. In evaluating response duration, non-responders will be excluded from analysis.

In addition, correlation analyses will be performed to assess the expression of TRAIL receptor in CTCs prior, during and upon progression of disease. Formal statistical tests will be performed based on the outcome types and the biomarker quantification.

Safety and Tolerability by NCI CTCAE v5.0 will be assessed by frequency tables. Also, metabolic indices in patients with metastatic TNBC treated with ONC-201 and a methionine-restricted diet will be assessed by frequency tables and descriptive statistics.

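### CTC endpoint: Section 13.7.2 names correlation analyses, but the hypothesis in Section 8.2 is a within-patient rise in TRAIL-receptor expression and a fall in CTC number

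*Combined protocol and SAP*

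**What the plan says.** Secondary objective 2.2.5 is "To assess the expression of TRAIL receptor in CTCs prior, during and upon progression in patients with metastatic TNBC" on the study regimen. Section 8.2 gives the hypothesis a direction: "We hypothesize that treatment with MR diet will increase the expression of TRAIL receptors on CTCs and reduce the number of CTCs". The sampling suits a paired analysis. In the same section, "CTCs will be collected at baseline, on day 5 of cycle 2, and at end of treatment", and "If the CTC sample is not collected at baseline, the remaining samples should not be collected", so every later sample should have a baseline partner.

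Section 13.7.2 gives the analysis in two sentences. The first is that "correlation analyses will be performed to assess the expression of TRAIL receptor in CTCs prior, during and upon progression of disease". The second is "Formal statistical tests will be performed based on the outcome types and the biomarker quantification". No test, contrast, scale or rule for missing samples follows, and CTC number is not mentioned in Section 13.7.2.

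The CTC work is conditional. Section 1.6 says that "CTCs will be drawn and analyzed if funding is secured". Section 8.2 limits draws to sites with the resources for them and does not count a missed sample as a deviation.

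**The concern.** The hypothesis is about movement in level within a patient. A correlation between two time points asks whether patients who were high at one are also high at the other. That is a different question, and its answer carries no information on whether the average rose or fell. A regimen that raised receptor expression equally in every patient and one that left it untouched would give the same coefficient.

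What is at stake is the mechanistic reading of the trial. Sections 1.4 and 1.7 rest on methionine restriction raising TRAIL-R2, and the CTC samples are the planned on-treatment look at this in patients. If the method is chosen once the data are in hand, there are many options. Section 1.6 lists three targets (TRAIL, TRAIL-R1, TRAIL-R2), each read by immunofluorescence and by mRNA. With CTC count that makes 3 × 2 + 1 = 7 measures, and two contrasts with baseline give 7 × 2 = 14 possible comparisons. None is marked as the main one.

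**Working it through.** The documents give no sample size, power, effect size or SD for the CTC endpoint, so there is no stated figure to reproduce. Two checks apply.

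**1. Does a correlation between time points respond to a shift?**

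Let X be the baseline value, Y the on-treatment value and c a constant shift. Then Cov(X, Y + c) = Cov(X, Y) and SD(Y + c) = SD(Y), so r(X, Y + c) = r(X, Y) for any c. Ranks within Y are also unchanged, so Spearman's rho is the same. The paired statistic, t = mean(Y + c − X) / (s_d / √n), has c in its numerator.

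This was confirmed on three simulated data sets of n = 34, the maximum in Section 13.2. Each value had unit population SD, and shifts of 0, 0.5, 1 and 2 SD were added to every on-treatment value:

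| Data set | Pearson r, all four shifts | Spearman rho, all four shifts | Paired p, no shift | Paired p, 0.5 SD shift |
|---|---|---|---|---|
| A | 0.7074 | 0.6183 | 0.24 | 0.006 |
| B | 0.5804 | 0.5532 | 0.91 | 0.003 |
| C | 0.7549 | 0.6923 | 0.74 | 0.0001 |

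Neither coefficient moves at all. The paired test picks up a shift of half an SD each time.

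**2. What could a paired analysis show at feasible numbers?**

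Assumptions not in the documents: two-sided 5% level, 80% power, differences roughly normal after transformation, and 10 to 34 complete pairs. The upper end is the trial maximum. The true number is unknown because collection is conditional.

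- Detectable mean change δ, in SDs of the differences: solve P(|T| > t(0.975, n−1)) = 0.80, where T is noncentral t with n−1 degrees of freedom and noncentrality δ√n.
- 95% CI half-width, in the same unit: t(0.975, n−1) / √n. For n = 20 this is 2.093 / 4.472 = 0.47.

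| Complete pairs | Detectable change | CI half-width |
|---|---|---|
| 10 | 1.00 | 0.72 |
| 13 | 0.85 | 0.60 |
| 20 | 0.66 | 0.47 |
| 27 | 0.56 | 0.40 |
| 34 | 0.50 | 0.35 |

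These figures describe the proposed analysis. They do not measure an error in the plan.

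**The case against.** The strongest reply is the second sentence of the plan, which promises formal tests suited to the outcome type. A paired test would fit that sentence, so the plan does not confine itself to correlation. This stands. A reader might infer that the CTC analysis cannot answer objective 2.2.5 at all, and the documents do not support that. The objective asks only that expression be assessed at several times, and a description at each time would meet its wording. The direction comes from Section 8.2. The sentence still names no test and no contrast, so it leaves the gap open.

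A second reply is that correlation may be meant loosely, or as correlation with outcome or with time. The text does not say which. Correlation with outcome would not test for a rise. Correlation with time could show a trend, but in its simple form it ignores the pairing that the sampling rule creates.

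A reader might also extend the point to the metabolic indices, since "metabolic indices in patients with metastatic TNBC treated with ONC-201 and a methionine-restricted diet will be assessed by frequency tables and descriptive statistics". That does not hold. Change from baseline is itself a descriptive statistic, the text does not limit the summaries to separate tables for each visit, and the objective for these indices carries no hypothesis.

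**Conclusion.** The method named for TRAIL-receptor expression does not test the hypothesis in Section 8.2, and the CTC-number half of that hypothesis has no stated analysis. The unspecified formal tests leave room for the right analysis without committing to it. The result on correlation is exact for a uniform shift. The power figures rest on the assumed number of pairs and on roughly normal differences.

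The weight is modest. The endpoint is secondary and depends on funding, and neither the two-stage response-rate decision nor the safety analysis is touched. This is a free improvement.

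Two limits apply even to the better analysis. No draw is tied to progression: the third sample is at end of treatment, which the study calendar places 35 ± 5 days after the last dose whatever the reason for stopping. And with one arm, a paired change describes the combination and not the diet alone. Section 1.5.2 itself describes ONC201 as acting on the DR5 receptor gene.

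**What to change.** In Section 13.7.2, replace the correlation sentence with text to this effect:

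- If CTCs are collected, the main CTC analysis is within-patient change from baseline to cycle 2 day 5. Change from baseline to end of treatment is the second contrast, with progression status at that visit noted.
- The measures are CTC count, TRAIL-R1 and TRAIL-R2. State which readout (immunofluorescence or mRNA) is used for the main analysis.
- The test is a Wilcoxon signed-rank test, or a paired t-test on the log scale, with the estimated change and its 95% CI. If the log scale is used for counts, state how a zero count is handled.
- Report the number of complete pairs for each contrast. State that expression is undefined where no CTCs are captured, and report how many samples this affects. If CTC number falls as hypothesised, such samples will become more common.
- Keep correlation or similar measures of association for relating CTC findings to response or PFS.

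The cost is a few sentences in the analysis plan. No visits, draws or patients are added beyond the conditional collection that the protocol already describes.

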### 13.7.3 Analysis plans for exploratory objectives

Kaplan-Meier methodology will be used to summarize time-to-event data, such as time to development of brain metastases or worsening of brain metastases in patients with metastatic TNBC treated with ONC-201 with a methionine-restricted diet. Graphical techniques (e.g., waterfall plots, KM curves, line plots) may be used when such methods are appropriate and informative.

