**2.3 Exploratory Objective:**

2.3.1 To determine time to development of brain metastases or worsening of brain metastases in patients with metastatic TNBC treated with ONC201 with a methionine-restricted diet.

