## 7. STUDY CALENDARS AND EVALUATIONS

Cycle = 21 days	Screening	Cycle 1	Cycle 2	Odd # cycles Begin at Cycle 3	Even # cycles Begin at Cycle 4	End of Treatment	Long-term Follow-up
	-28 days	Day 1 +/- 2 days	Day 1 +/- 2 days	Day 1 +/- 2 days	Day 1 +/- 2 days	35 days from last dose of study treatment +/- 5 days	Every 3 months (+/- 7 days) for 2 years from EOT
Informed consent	X						
Medical history	X						
Diagnosis and staging	X						
Physical Exam	X	X 	X	X	X	X	
Vital signs, wt, waist circumference  , ECOG performance status	X	X 	X	X	X	X	
AEs & concomitant medications, drug diary review 	X	X	X	X	X	X	
LABORATORY ASSESSMENTS							
CBC with differential (minimum to include: Hgb, WBC, Plt, ANC)	X	X 	X	X	X	X	
CMP 	X	X 	X	X	X	X	
Blood for metabolic indices 		X	X		X	X	
Homocysteine/cysteine 		X		X		X	

Cycle = 21 days	Screening	Cycle 1	Cycle 2	Odd # cycles Begin at Cycle 3	Even # cycles Begin at Cycle 4	End of Treatment	Long-term Follow-up
	-28 days	Day 1 +/- 2 days	Day 1 +/- 2 days	Day 1 +/- 2 days	Day 1 +/- 2 days	35 days from last dose of study treatment +/- 5 days	Every 3 months (+/- 7 days) for 2 years from EOT
Pregnancy test (serum) 	- 7 days	X 					
Diet/Exercise Diary		X	X	X	X		
24 Hour Dietary Recall Form		X					
DISEASE ASSESSMENTS							
CT chest, CT or MRI of abdomen and pelvis 	X				X 		X
MRI brain	X 						
Bone scan	X 				X 		
TREATMENT EXPOSURE							
ONC201		Days 3 and 4, weekly	Days 3 and 4, weekly	Days 3 and 4, weekly	Days 3 and 4, weekly		
MR diet		Days 1 - 5 weekly	Days 1 - 5 weekly	Days 1 - 5 weekly	Days 1 - 5 weekly		
CORRELATIVE STUDIES (SPECIMEN COLLECTION)							
Archival Tissue 	X						
Circulating tumor cells		X 	X 			X 	
Plasma methionine & methionine metabolites		X 	X 		X 	X 	
FOLLOW-UP							
Survival							X

- (1) Blood will be taken to assess metabolic indices at baseline, cycle 2 day 5, then day 5 of every other cycle, and at end of treatment. Indices are fasting: glucose, insulin, IGF-1, and leptin levels. If necessary, these labs may be drawn as early as day 2, but prefer to be as close to day 5 as possible without going over.

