- (2) Blood will be taken to assess plasma methionine levels at baseline, cycle 2 day 5, then day 5 of every other cycle, and at end of treatment. Subjects must be fasting. If necessary, these labs may be drawn as early as day 2, but prefer to be as close to day 5 as possible without going over.
- (3) If clinically indicated.
- (4) Optional biopsy prior to study entry.
- (5) Blood for circulating tumor cells will be taken at baseline, day 5 of cycle 2, and at end of treatment. If necessary, these labs may be drawn as early as day 2, but prefer to be as close to day 5 as possible without going over.
- (6) For women of childbearing potential. To be completed within 7 days of randomization. Must be repeated at cycle 1 day 1 if not completed in previous 7 days.
- (7) Subjects whose treatment is interrupted or permanently discontinued due to an adverse event (including lab values) should be followed per section 11.1.1.
- (8) Waist circumference, optional if not possible due to site limitations. Not required at screening.
- (9) CMP to include sodium, potassium, chloride, carbon dioxide, glucose, BUN, creatinine, calcium, albumin, total protein, alkaline phosphatase, aspartate aminotransferase (AST), alanine aminotransferase (ALT), and total bilirubin.
- (10) CT chest with or without contrast and CT with contrast or MRI of Abdomen/Pelvis to be completed during screening and  $\leq$  7 days prior to every third cycle starting at cycle four (approximately every 9 weeks; e.g. cycles 4, 7, 10, etc.). If subjects discontinue study treatment prior to disease progression, scans during follow-up will be completed per standard of care, but RECIST measurements must be completed until disease progression or start of new anti-cancer therapy.
- (11) Homocysteine/cysteine level at: baseline and every 3 cycles while on study (C1, C4, C7, etc.) and at end of treatment.
- (12) One block or 10 unstained slides.
- (13) labs/physical exam/ECOG PS does not need to be repeated if done within 7 days prior to C1D1

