#### **9.5 Evaluation of Target Lesions**

**NOTE:** In addition to the information below, also see section 4.3.2 in the international criteria proposed by the Response Evaluation Criteria in Solid Tumors (RECIST) Committee, version 1.1 (Eur J Cancer 45;2009:228-247) for special notes on the assessment of target lesions.

Complete Response (CR)	Disappearance of all target lesions. Any pathological lymph nodes (whether target or non-target) must have reduction in short axis to <10 mm.
Partial Response (PR)	At least a 30% decrease in the sum of the diameters of target lesions, taking as reference the baseline sum diameters
Progressive Disease (PD)	At least a 20% increase in the sum of the diameters of target lesions, taking as reference the smallest sum on study (this includes the baseline sum if that is the smallest on study). In addition to the relative increase of 20%, the sum must also demonstrate an absolute increase of at least 5 mm. (Note: the appearance of one or more new lesions is also considered progressions).
Stable Disease (SD)	Neither sufficient shrinkage to qualify for PR nor sufficient increase to qualify for PD, taking as reference the smallest sum diameters while on study

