### 9.8.6 Progression-Free Survival

A measurement from the date of treatment initiation until the criteria for disease progression is met as defined by RECIST 1.1 or death occurs. Subjects who have not progressed will be right-censored at the date of the last disease evaluation.

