### 9.8.7 Overall Survival

Overall survival is defined by the date of treatment initiation to date of death from any cause.

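### Time to brain metastases is summarised by Kaplan-Meier alone, with no rule for death without a brain event; if those deaths are censored, one minus the curve overstates the proportion affected while brain status is followed

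*Combined protocol and SAP*

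**What the plan says.** The exploratory objective in section 2.3 is "To determine time to development of brain metastases or worsening of brain metastases in patients with metastatic TNBC". The event is non-fatal, and no time origin or censoring rule accompanies it. Section 13.7.3 gives the analysis: "Kaplan-Meier methodology will be used to summarize time-to-event data, such as time to development of brain metastases or worsening of brain metastases". Beyond that it offers only optional graphics.

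The plan is more explicit for its other time-to-event measures. PFS (section 9.8.6) runs from treatment initiation "until the criteria for disease progression is met as defined by RECIST 1.1 or death occurs", with censoring at the last disease evaluation. For OS (section 9.8.7), "Overall survival is defined by the date of treatment initiation to date of death from any cause". For duration of response (section 13.7.2), "Subjects who do not relapse will be censored at the day of the last objective tumor assessment". None of these rules is extended to brain metastases. Cox regression appears in the synopsis, with PFS and OS as examples, and as an option in section 13.7.2. Neither mention is tied to this endpoint, and neither would settle how death is treated.

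On ascertainment, the calendar in section 7 lists brain MRI at screening only, if clinically indicated. The scheduled on-study scans are "CT chest, CT or MRI of abdomen and pelvis". A brain lesion found on study would still count towards progression, because "the appearance of one or more new lesions is also considered progressions" (section 9.5). After treatment stops, "RECIST measurements must be completed until disease progression or start of new anti-cancer therapy". Survival and first subsequent therapy are then followed every 3 months for 2 years (section 6.3).

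**The concern.** Kaplan-Meier needs a decision about patients who leave the risk set. A patient who dies without a brain event can no longer have one. Censoring that patient treats her as still able to have the event later. The curve then describes the brain-event hazard validly, but one minus the curve is not the share of patients affected.

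Because the rule is unwritten, the same data could be reported as three different quantities:

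- with deaths censored, one minus Kaplan-Meier;
- with deaths competing, a cumulative incidence;
- with death counted as part of the event, brain-metastasis-free survival.

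Section 1.1 gives a median survival of 13 months in advanced TNBC, so deaths will not be rare over the planned follow-up. What is at stake is the reading of one exploratory curve. The ORR decision rule does not use it.

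**Working it through.** The plan states no figure for this endpoint, so there is none to reproduce. The check compares the candidate estimates under stated assumptions.

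**Inputs.** The documents supply N = 34 and, as background, a median survival of 13 months. That median is all-cause, so it is only a proxy for death without a brain event. Assumed here:

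- constant hazards;
- one minus Kaplan-Meier at 12 months, x, of 10%, 20% or 30%;
- median time to death without a brain event, M, of 9, 13, 18 or 24 months.

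**Formulas.** The brain-event hazard is b = −ln(1−x)/12 and the death hazard is d = ln 2/M, both per month. With deaths censored, 1−KM(t) = 1−exp(−bt). The proportion with a brain event is CIF(t) = b/(b+d) × [1−exp(−(b+d)t)].

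**Central case (x = 20%, M = 13).** b = 0.01860 and d = 0.05332.

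- At 6 months, 1−KM = 10.6% and CIF = 9.1%, a gap of 1.5 points. Over 34 patients that is 3.6 against 3.1 patients.
- At 12 months, 1−KM = 20.0% and CIF = 14.9%, a gap of 5.1 points.
- Counting death as an event gives 1−exp(−(b+d)t), which is 35.0% at 6 months and 57.8% at 12 months. That is a different quantity altogether.

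**Range over all 12 combinations.**

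| Month | Gap (points) | Ratio 1−KM to CIF |
|---|---|---|
| 6 | 0.4 to 3.2 | 1.09 to 1.25 |
| 12 | 1.5 to 9.9 | 1.17 to 1.52 |

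The smallest gaps come from x = 10%, M = 24 (5.13% against 4.72% at 6 months). The largest come from x = 30%, M = 9 (16.33% against 13.17% at 6 months).

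**Sampling error.** If all 34 patients were followed to 6 months, the 95% half-width would be 1.96 × √(0.106 × 0.894/34) = 0.103, about 10 points. If brain status is recorded only to progression, with an assumed median of 2 to 6 months (hazard p = ln 2/median), the expected number at risk is 34 × exp(−(b+d+p)t). That is 2.8 to 11.0 patients at 6 months and 0.2 to 3.6 at 12 months. The Greenwood half-width at 6 months is then 14 to 21 points.

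**Which deaths should compete.** Suppose brain status ends at progression with median 2 to 6 months, but every death over 24 months is counted as competing. In simulation of the central case the 6-month estimate drops to about 5% to 7% against a true 9.1%. Patients whose brain status is no longer known would be sitting in the risk set. Counting deaths only while status is followed returns 9.1%.

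**If the hazard changes at progression.** Take the central case with the brain-event hazard doubled after progression, status recorded only to progression, and median progression at 3 or 4 months. True incidence at 6 months is 12.7% or 12.0%. Kaplan-Meier gives 10.6% and cumulative incidence under follow-up gives 9.1%, so both are too low. With a 1.5-fold rise the true figures are 10.9% and 10.6%, and Kaplan-Meier is close to right by accident.

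**The case against.** The strongest reply is that the plan never takes the step that causes the harm. It says only that the data will be summarised. It neither states that deaths are censored nor promises a proportion, and Kaplan-Meier with deaths censored is a legitimate description of the hazard. That is correct, and it is why the point is conditional. A reader might infer that the trial will report an inflated brain-metastasis rate; the documents do not support that. What remains is that the plan does not say which quantity is meant.

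The second reply concerns direction. A reader might infer that Kaplan-Meier must overstate the total incidence of brain metastases. The last calculation shows otherwise: if recording stops at progression and the hazard then rises, Kaplan-Meier is low and cumulative incidence is lower still. The direction is certain only for the period in which brain status is followed.

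Third, it is tempting to say that brain status stops being recorded at progression. The calendar and section 6.3 set the minimum for RECIST measurement, and section 15.2 allows selected standard-of-care data to be captured according to study objectives, of which this is one. Later brain events may therefore be on record. For that reason the fix should not censor automatically at progression or new therapy, nor impose a fixed window after the last scan.

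Finally, the gap is small next to the uncertainty. That stands, and it limits the weight of the point, but it does not tell a reader what the curve means.

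**Conclusion.** The point holds as a minor one. Kaplan-Meier is the only method named for a non-fatal event in a disease with substantial mortality, and death without that event has no stated treatment. If such deaths are censored and the curve is read as a proportion, it is too high over the period in which brain status is followed. The size rests on constant hazards and on assumed brain-event and death rates, because the documents give no brain-event rate. The gap is within sampling error for 34 patients, and the 12-month figures matter only if brain status is followed that long. Whether Kaplan-Meier is above or below total incidence depends on what happens after progression, which the documents do not settle. PFS, OS and the ORR decision are unaffected.

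**What to change.** In section 13.7.3:

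- Measure from treatment initiation, as for PFS and OS.
- Report the Aalen-Johansen cumulative incidence of new or worsening brain metastases with 95% confidence intervals.
- Treat death without a prior brain event as a competing event while brain or disease status is still being followed.
- Censor all other patients at the date brain or disease status was last known.
- Include every brain event recorded, including any captured after progression.
- Report numbers at risk and the number of deaths after the last-known date.
- State that brain imaging is only as clinically indicated, so events may be under-ascertained and censoring may be informative.

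Keep Kaplan-Meier for PFS and OS.

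The cost is a short paragraph and a little more analysis work, with no new procedures. The reported figure will be slightly lower. It describes incidence while under follow-up and does not recover events that were never recorded. If the brain-event hazard rises after status is lost, it will lie further below total incidence than Kaplan-Meier does (9.1% against 10.6% in the doubled-hazard example), so the stated limitation has to accompany it.
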